#### Use in Pregnancy

If a subject inadvertently becomes pregnant while on study treatment, the subject will immediately be removed from the study treatment. The site will contact the subject at least monthly and document the subject's status until the pregnancy has been completed or terminated. The outcome of the pregnancy will be reported to Gilead Sciences, Inc. and Genentech without delay, especially if the outcome is a serious adverse experience (e.g., death, abortion, congenital anomaly, or other disabling or life-threatening complication to the mother or newborn).

If a male subject impregnates his female partner the study personnel at the site must be informed immediately and the pregnancy reported to [Gilead Sciences, Inc.](#) and Genentech and followed as described above.

#### Use in Nursing Women

It is unknown whether magrolimab is excreted in human milk. Since many drugs are excreted in human milk, and because of the potential for serious adverse reactions in the nursing infant, patients who are breast-feeding are not eligible for enrollment.

### **APPENDIX C: INHIBITORS AND INDUCERS OF CYP3A AND P-GP**

A comprehensive list of inhibitors can be found at the following website: <http://medicine.iupui.edu/clinpharm/ddis/table.aspx>. The general categorization into strong, moderate, and weak inhibitors according to the website and venetoclax FDA label is displayed below.

| Inhibitors of CYP3A   | Inducers of CYP3A  | Inhibitors of P-gp   |
|--|---|---|
| Strong inhibitors:
INDINAVIR
NELFINAVIR
RITONAVIR
CLARITHROMYCIN
ITRACONAZOLE
KETOCONAZOLE
NEFAZODONE
SAQUINAVIR
TELITHROMYCIN
CONIVAPTAN
POSACONAZOLE
VORICONAZOLE

Moderate inhibitors:
aprepitant
erythromycin
diltiazem
fluconazole
grapefruit juice
seville orange juice
verapamil | Weak inhibitors:
cimetidine

All other inhibitors:
amiodarone
azithromycin
chloramphenicol
boceprevir
ciprofloxacin
delavirdine
diethyl-dithiocarbamate
fluvoxamine
gestodene
imatinib
mibepradil
mifepristone
norfloxacin
norfluoxetine
star fruit
telaprevir
troleandomycin
voriconazole | carbamazepine
efavirenz
nevirapine
barbiturates
glucocorticoids
modafinil
oxcarbazepine
phenobarbital
phenytoin
pioglitazone
rifabutin
rifampin
St. John's Wort
troglitazone |

Source: <http://medicine.iupui.edu/clinpharm/ddis/table.aspx> and  
[https://www.accessdata.fda.gov/drugsatfda\\_docs/label/2016/208573s000lbl.pdf](https://www.accessdata.fda.gov/drugsatfda_docs/label/2016/208573s000lbl.pdf)

## **APPENDIX D: STUDY DRUG DIARY (OPTIONAL)**

Patient Name: \_\_\_\_\_ Cycle: \_\_\_\_\_

### Instructions:

- Use this diary to record all doses of oral study medication taken.
- You should bring this study drug diary and each of your study medications (including leftover pills and empty bottles) with you to each clinic visit.
- Contact us if you have any side effects or before starting any new medications or over-the-counter drugs.
- If you have questions at any time, please contact your doctor or nurse.

### Study Drugs:

The study medications should be taken as follows; the doses will be assigned to you by your doctor:

|              |   |
|--------------|---|
| Venetoclax   | Venetoclax tablets to be taken by mouth, with a glass of water and food |
| Magrolimab   | Magrolimab is given by IV, in the clinic                                |
| Obinutuzumab | Obinutuzumab is given by IV, in the clinic                              |

### Additional Information:

- The venetoclax should be taken at about the same time each day
- If you do not remember to take all or any of the medications on any day, please tell us. Do not make-up the dose or take extra the following day to make-up for the missed dose.
- If you vomit after taking a dose, you should not take another dose that day. However, if vomiting occurs within 15 minutes after taking venetoclax and all expelled tablets are still intact, another dose may be given.

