**Table 10: Intrapatient ramped-up dose-escalation schedule for venetoclax in MZL, MCL and CLL patients**

| Week of safety ramp-up period | Patients with MZL, MCL and CLL (Arms 2 and 4) |                |
|-------------------------------|---|----------------|
|                               | DL(-1):
200 mg                             | DL1:
400 mg |
| 1                             | 20 mg   | 20 mg          |
| 2                             | 50 mg   | 50 mg          |
| 3                             | 100 mg  | 100 mg         |
| 4                             | 200 mg  | 200 mg         |
| 5                             | 200 mg  | 400 mg         |

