### **3.2 DRUG ADMINISTRATION**

Treatment schedule from Cycles 1 to 12 is provided below ([Table 11](#) and [Table 12](#) for dose-finding and dose-expansion respectively). A flexibility window between cycles of -3/+7 days is allowed due to scheduling or other administrative reasons; additional delays may apply based on toxicities.

Magrolimab doses will be calculated based on actual body weight measured at the most recent clinical assessment prior to administration. Patients will be encouraged to complete and return an optional drug diary as a memory aid to help document the date and time of all self-administered study drugs ([Appendix D](#)). This drug diary as well as study drug containers and any unused study drug should be returned to the research team at the end of each cycle of therapy.

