### 3.2.3 Venetoclax administration

Venetoclax should be taken with a meal. If vomiting occurs within 15 minutes after taking venetoclax and all expelled tablets are still intact, another dose may be given. Otherwise, no replacement dose is to be given. In cases where a dose of venetoclax is missed or forgotten, the patient should take the dose as soon as possible and ensure that the minimal interval between the current dose and the next dose is at least 16 hours in order to avoid excessive drug accumulation after the next dose.

Venetoclax will be dispensed to patients in bottles. All doses of venetoclax taken in the clinic or day hospital should be taken from the bottle dispensed to the subject. Unused venetoclax tablets dispensed during previous visits must be returned. Returned tablets must not be re-dispensed to anyone.

Patients will be encouraged to complete and return an optional drug diary as a memory aid to help document the date and time of all self-administered study drugs ([Appendix D](#)).

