### EXAMPLES – Study Drug Diary (Cycle 2-12):

These are examples of how you might take the study drugs:

- Day 1: Come to clinic. Take the venetoclax when advised by the study staff.
- Days 2 through 14: Take the venetoclax.
- Day 15: Come to clinic. Take the venetoclax when advised by the study staff.
- Days 16-28: Take the venetoclax.

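### Section 3.2.3 and the Appendix D diary give opposite instructions for a missed venetoclax dose, and the printed diary form does not fit Cycle 1 of Arms 1, 2 and 4

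*Combined protocol and SAP*

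**What the plan says.** **Missed doses.** Section 3.2.3 (Venetoclax administration) states: "In cases where a dose of venetoclax is missed or forgotten, the patient should take the dose as soon as possible" and adds that the patient should "ensure that the minimal interval between the current dose and the next dose is at least 16 hours". Appendix D, under Additional Information, asks the patient to report a forgotten dose and then says: "Do not make-up the dose or take extra the following day to make-up for the missed dose". The exception for tablets vomited intact within 15 minutes is the same in both places.

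**Role of the diary.** Section 3.2.3 introduces it directly: "Patients will be encouraged to complete and return an optional drug diary as a memory aid". The form's own instructions are broader: "Use this diary to record all doses of oral study medication taken". Section 3.2 adds that the diary, the containers and any unused drug "should be returned to the research team at the end of each cycle of therapy".

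**Layout of the form.** The examples are headed "EXAMPLES – Study Drug Diary (Cycle 2-12)". The table has one row for each of Days 1 to 28. Clinic infusions are pre-printed on Day 1 (obinutuzumab and magrolimab) and Day 15 (magrolimab).

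**Schedule.** Section 2.3.2.2 and Tables 11 and 12 set Cycle 1 at 35 days for MZL, MCL and CLL patients (Arm 2, and Arm 4 covering Cohorts 4 to 6). Table 10, "Intrapatient ramped-up dose-escalation schedule for venetoclax in MZL, MCL and CLL patients", gives the weekly venetoclax steps. Section 3.1.4 sets the Arm 2 DLT window at C1D1 to C1D35.

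**The concern.** Venetoclax is the only study drug taken at home and the only one whose dose the trial selects. If the protocol body and the patient's form disagree about a forgotten dose, two patients with the same lapse can receive different amounts of drug for a reason unrelated to tolerance or disease.

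The form also gives no place to record the last week of the ramp-up cycle. In Arm 2 at dose level 1, that week is the first and only one at target dose before the DLT decision. A dated intake record is most useful there when someone has to judge whether an event followed a taken dose or a missed one.

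**Working it through.** The plan gives no figure to reproduce. The check compares the texts and makes a few counts.

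**1. Missed dose**

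- Inputs: once-daily dosing (Table 7), hence a nominal 24-hour interval; minimum gap of 16 hours to the next dose (Section 3.2.3).
- Assumption: the next dose stays at its usual time, in line with the diary's advice to dose at a steady time of day.
- Latest permitted delay under Section 3.2.3: 24 − 16 = **8 hours**.
- A patient who remembers 4 hours late has 24 − 4 = 20 hours to the next dose. Since 20 ≥ 16, Section 3.2.3 directs that the dose be taken. The diary directs that it not be made up.
- A patient who remembers 10 hours late has 24 − 10 = 14 hours, which is under 16. If the next dose is not moved, both texts then lead to no late dose.

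The two texts therefore conflict for delays up to 8 hours and lead to the same action beyond that, on the stated assumption.

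**2. Rows against cycle length**

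- Cycle 1 in Arms 2 and 4: 35 days. Rows on the form: 28.
- Days without a row: 35 − 28 = **7** (Days 29-35), and 7/35 = **20%** of the cycle.
- Patients with a 35-day Cycle 1: up to 12 in Arm 2, and 6 + 12 + 6 = 24 in Cohorts 4, 5 and 6.

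**3. What those seven days are in Arm 2 (Tables 10 and 11)**

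| Dose level | Days 22-28 | Days 29-35 | Target days in the DLT window that lack a row |
|---|---|---|---|
| DL1 (400 mg) | 200 mg | 400 mg | 7 of 7 |
| DL(-1) (200 mg) | 200 mg | 200 mg | 7 of 14 |

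The loss of every target-dose row applies only to dose level 1, where six evaluable patients are planned. At dose level −1 the target is reached in Week 4, inside the printed rows. Arm 4 patients are outside the DLT assessment.

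**4. Pre-printed infusion days against Cycle 1**

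| | Magrolimab | Obinutuzumab |
|---|---|---|
| Diary form | 1, 15 | 1 |
| Arms 1 and 2, Cycle 1 (Table 11) | 2, 8, 15, 22 | 1, 2, 8, 15 |
| Arm 4, Cycle 1 (Table 12) | 1, 15 | 1 |

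The form is wrong for Cycle 1 of both dose-finding arms and right for Cycle 1 of Arm 4. Arm 1 Cycle 1 lasts 28 days, so its rows fit and only the infusion days do not.

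**The case against.** **The conflict may be only apparent.** The diary speaks of forgetting on a given day and of taking extra the next day, whereas Section 3.2.3 covers a late dose with a protected interval. This narrows the conflict but does not remove it. The diary's ban on making up the dose stands apart from its ban on extra tablets the next day, and it makes no allowance for a late dose on the same day. The advice to dose at a steady time is not itself a contradiction.

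**A reader might infer that Section 3.2.3 sets no limit on lateness.** The 16-hour rule is an effective limit, as calculated above.

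**A reader might infer that the diary is the only instruction patients hold.** The documents do not show this. Consent pages are not in the public copy, bottles are labelled, and some patients may not use an optional diary at all.

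**A reader might infer that intake on Days 29-35 cannot be recorded, or is known only from a tablet count.** That goes too far. The form has a blank cycle field and columns for date and comments, so a second sheet would serve. Patients are asked to report forgotten doses and to bring the diary and leftover tablets to each visit. The plan also schedules contact around that week: twice-weekly blood counts through Cycle 1 of the dose-finding arms (Section 3.2.1), and recommended pre-dose chemistry at later ramp-up steps (Table 19), which include Day 29 at dose level 1. What remains is that the printed form has no rows for that week.

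**A reader might infer that the DLT decision is compromised**, since one missed dose is 1/7 (14%) of the scheduled 400 mg days in the window. That fraction enters no rule. The DLT definition covers toxicity across the whole of Cycle 1, the replacement rule in Section 3.1.1 sets no intake threshold, and no analysis in Section 10 uses diary data.

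**Conclusion.** Both defects are present and both are small. The missed-dose instructions contradict each other for a dose remembered up to about 8 hours late, assuming once-daily dosing with the next dose left at its usual time. The printed diary suits the 28-day Cycles 2-12. It lacks rows for 7 of the 35 days of Cycle 1 in Arms 2 and 4, and it shows the wrong infusion days for Cycle 1 of Arms 1 and 2. In Arm 2 at dose level 1, the missing rows cover all seven scheduled days at 400 mg within the DLT window.

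The consequence is limited to consistency of home dosing and the day-level intake record. Sample size, endpoints, dose-finding rules and analyses are unaffected. The finding about the form rests on the public copy, in which Appendix D contains a single diary form; a Cycle 1 sheet held elsewhere would settle that part but not the conflict over missed doses.

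**What to change.** 1. Reconcile Section 3.2.3 and Appendix D so that both give a single missed-dose instruction. Which one is a clinical decision, and this review takes no position on it.
2. Add a 35-day Cycle 1 diary sheet for Arms 2 and 4, with rows to Day 35.
3. Give the Cycle 1 sheets for Arms 1 and 2 infusion days that match Table 11. The Arm 2 sheet can meet items 2 and 3 together. The Arm 4 infusion days need no change.

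The cost is one reconciled sentence in an amendment and revised patient sheets, with little added burden on patients. Making the diary compulsory is not part of this fix: the protocol presents it as an optional memory aid, no stated objective needs daily intake data, and compulsion would resolve neither discrepancy.

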### EXAMPLES – Study Drug Diary (Cycle 2-12):

These are examples of how you might take the study drugs:

- Day 1: Come to clinic. Take the venetoclax when advised by the study staff.
- Days 2 through 14: Take the venetoclax.
- Day 15: Come to clinic. Take the venetoclax when advised by the study staff.
- Days 16-28: Take the venetoclax.

### **STAFF USE ONLY**

Date returned/reviewed: \_\_\_\_\_ Staff member: \_\_\_\_\_

Notes/Comments:

Please record the dose/number of pills of each study drug taken in the table below:

| Cycle Day | Date | Study Drugs |                     |                   | Comments |
|------------------|-------------|--------------------|---------------------|-------------------|-----------------|
|                  |             | Venetoclax  | Obinutuzumab | Magrolimab |                 |
| 1                |             |                    | In Clinic, IV       | In Clinic, IV     |                 |
| 2                |             |                    |                     |                   |                 |
| 3                |             |                    |                     |                   |                 |
| 4                |             |                    |                     |                   |                 |
| 5                |             |                    |                     |                   |                 |
| 6                |             |                    |                     |                   |                 |
| 7                |             |                    |                     |                   |                 |
| 8                |             |                    |                     |                   |                 |
| 9                |             |                    |                     |                   |                 |
| 10               |             |                    |                     |                   |                 |
| 11               |             |                    |                     |                   |                 |
| 12               |             |                    |                     |                   |                 |
| 13               |             |                    |                     |                   |                 |
| 14               |             |                    |                     |                   |                 |
| 15               |             |                    |                     | In Clinic, IV     |                 |
| 16               |             |                    |                     |                   |                 |
| 17               |             |                    |                     |                   |                 |
| 18               |             |                    |                     |                   |                 |
| 19               |             |                    |                     |                   |                 |
| 20               |             |                    |                     |                   |                 |
| 21               |             |                    |                     |                   |                 |
| 22               |             |                    |                     |                   |                 |
| 23               |             |                    |                     |                   |                 |
| 24               |             |                    |                     |                   |                 |
| 25               |             |                    |                     |                   |                 |
| 26               |             |                    |                     |                   |                 |
| 27               |             |                    |                     |                   |                 |
| 28               |             |                    |                     |                   |                 |

## APPENDIX E: CAIRO-BISHOP DEFINITION FOR TLS

The Cairo-Bishop definition proposed in 2004 (**Table 21**), provided specific laboratory criteria for the diagnosis of TLS both at presentation and within seven days of treatment. It also incorporated a grading system to help delineate the degree of severity of TLS (**Table 22**).

**Table 21: Cairo-Bishop laboratory TLS definition**

| Parameter  | Value                                     | Change from baseline |
|------------|---|----------------------|
| Uric acid  | $\geq 476$ micromol/L (8 mg/dL)           | 25% increase         |
| Potassium  | $\geq 6.0$ mmol/L (or 6 mEq/L)            | 25% increase         |
| Phosphorus | $\geq 1.45$ mmol/L (4.5 mg/dL) for adults | 25% increase         |
| Calcium    | $\leq 1.75$ mmol/L (7 mg/dL)              | 25% increase         |

**Laboratory TLS** is defined as any two or more abnormal serum values, as mentioned in the above table (**Table 21**), present within three days before or seven days after instituting therapy in the setting of adequate hydration (with or without alkalinization) and use of a hypouricemic agent.

**Clinical TLS** is defined as laboratory TLS plus one or more of the following that was not directly or probably attributable to a therapeutic agent: increased serum creatinine concentration ( $\geq 1.5$  times the upper limit of normal [ULN]), cardiac arrhythmia/sudden death, or a seizure.

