#### 4.1.2.2 Recommendations for Initial Management and TLS Prevention

##### 4.1.2.2.1 First Dose of Venetoclax or Dose Escalation

Within the first 24 hours after either the first dose or dose escalation, if laboratory criteria for TLS (**Table 21**) are met, the patient should be hospitalized for monitoring and the investigator notified. No additional venetoclax doses should be administered until resolution.

- Availability of emergency dialysis should be ensured

- Intravenous (IV) fluids should be initiated at a rate of at least 1 mL/kg/h rounded to the nearest 10 mL (target 150-200 mL/hr; < 50 mL/hr). Modification of fluid rate should also be considered for individuals with specific medical needs.

The management recommendations below focus on the minimum initial responses required. If a diagnosis of TLS is established, ongoing intensive monitoring and multidisciplinary management will be as per institutional protocols.

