#### 4.1.2.3 For any occurrence of laboratory TLS:

- Withhold the next day's venetoclax dose. If resolved within 24 to 48 hours of last dose, resume at the same dose.
- For any blood chemistry changes requiring more than 48 hours to resolve, resume at a reduced dose.
- For any events of clinical TLS, resume at a reduced dose following resolution

In addition to the above, additional recommendations for patients with chronic lymphocytic leukemia/ small lymphocytic lymphoma receiving first dose of venetoclax:

- For potassium increase  $\geq$  0.5 mmol/L from baseline, AND  $>$  5.0 mmol/L, recheck potassium, phosphorus, uric acid, calcium, and creatinine and follow guidelines per Section **4.1.2.2.1**
- For phosphorus increase of  $>$  0.5 mg/dL AND  $>$  4.5 mg/dL, administer phosphate binder and recheck potassium, phosphorus, uric acid, calcium, and creatinine.

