#### 4.1.2.4 Tumor Lysis Syndrome from Obinutuzumab (Precautions During Cycle -2 of Dose-Expansion)

TLS, including fatal TLS, has been reported with obinutuzumab. Patients with CLL or MCL who are treated with the combination of obinutuzumab and magrolimab are considered at risk of TLS if they have lymph nodes  $\geq$  5 cm or ALC  $\geq$   $25 \times 10^9/L$ , splenomegaly, renal dysfunction (Cr. Cl.  $<$  70 mL/min) or baseline clinical chemistry abnormalities consistent with TLS as per **Table 21**. Patients during dose-finding portion of the study will commence obinutuzumab in combination with venetoclax, and the guidelines outlined in Section **4.1.2** must be followed. During dose-expansion phase, however, patients will commence obinutuzumab in combination with magrolimab during Cycle -2 of the window period. CLL and MCL patients considered at risk of TLS when treated with obinutuzumab in combination with magrolimab must be treated and monitored as follows:

- Patients should receive IV or oral hydration (approximately 3 L per day recommended) starting 1 day before the first dose of obinutuzumab and should continue until and including D8 (approximately 3 L per day recommended).
- Patients should be treated with uricostatics (such as allopurinol) or urate oxidase (such as rasburicase) as per label or local guidance.
- Patients should undergo laboratory assessments for TLS (uric acid, calcium, phosphate, potassium, and creatinine) and the results must be known on the same day the sample was taken.
  - D1 of Cycle -2
  - D2 of Cycle -2
  - D3 of Cycle -2

- D8 of Cycle -2

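### Table 21 pairs a low calcium limit with a 25% increase from baseline, so the laboratory-TLS trigger can be wrong when calcium is the deciding value

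*Combined protocol and SAP*

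**What the plan says.** Section 4.1.2.1 adopts the TLS definition in Appendix E for this study. Table 21 of that appendix lists four analytes, each with a Value and a Change from baseline.

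- **Uric acid, potassium and phosphorus** have upper limits, for example potassium "\geq 6.0$ mmol/L (or 6 mEq/L", each with a 25% increase.
- **Calcium** has a lower limit, "\leq 1.75$ mmol/L (7 mg/dL", that is, at or below 1.75 mmol/L. Its change cell is also a 25% increase.

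Laboratory TLS "is defined as any two or more abnormal serum values, as mentioned in the above table". Clinical TLS "is defined as laboratory TLS plus one or more of the following" complications: raised creatinine, arrhythmia or sudden death, or seizure. Nothing says how the Value and Change columns combine.

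The table drives treatment decisions:

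- **Section 4.1.2.2.1.** If the Table 21 criteria are met within 24 hours of the first dose or of an escalation, "the patient should be hospitalized for monitoring and the investigator notified. No additional venetoclax doses should be administered until resolution".
- **Section 4.1.2.3.** Under its heading "For any occurrence of laboratory TLS", the next day's venetoclax dose is withheld. The same list adds: "For any events of clinical TLS, resume at a reduced dose following resolution".
- **Section 4.1.2.4.** CLL and MCL patients can be classed as at risk from obinutuzumab on "baseline clinical chemistry abnormalities consistent with TLS as per" Table 21.

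**The concern.** A rise moves calcium away from a lower limit, so the two cells of the calcium row point in opposite directions. In the other three rows they agree. The likely cause is that the change text was carried down the column without being reversed for calcium.

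Table 21 is the only place where the plan gives a calcium criterion for TLS. The additional CLL/SLL thresholds in Section 4.1.2.3 cover potassium and phosphorus only. A literal reading could therefore fail to start hospitalisation and the venetoclax hold in a patient whose calcium has fallen, or start them in a patient whose calcium has risen. Because clinical TLS is built on laboratory TLS, the reduced-dose restart inherits the error.

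The hazard is relevant here. Section 1.2.5.1 reports TLS in 10 of 56 CLL patients in a venetoclax dose-escalation cohort, with one case of dialysis and one sudden death. Under Section 3.1.5, FL patients start venetoclax at the target dose without a ramp-up.

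**Working it through.** **Inputs from the documents (Appendix E, Table 21):** calcium limit L = 1.75 mmol/L (7 mg/dL), a lower limit; change from baseline = 25% increase; laboratory TLS = at least two abnormal analytes.

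**Assumed input:** baseline calcium. The documents give no normal range, so baselines of 2.1 to 2.6 mmol/L are used for illustration.

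**Step 1: is the limit itself in error?** 1.75 mmol/L × 4.008 = 7.01 mg/dL, which matches the printed 7 mg/dL. The value cell is consistent, which leaves the direction of change as the fault.

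**Step 2: 'and' reading.** Calcium must rise by 25% and still be at or below the limit:

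1.25 × baseline ≤ 1.75, so baseline ≤ 1.75/1.25 = 1.40 mmol/L.

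A patient who falls from an assumed normal baseline to 1.75 or below never qualifies, so the row is practically unmeetable.

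**Step 3: 'or' reading.** A value at or below 1.75 counts correctly. The change criterion fails in two ways:

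- A 25% rise (to 1.25 × baseline) counts as a TLS abnormality.
- A 25% fall (to 0.75 × baseline) does not count unless it also reaches the limit. It stays above the limit when 0.75 × baseline > 1.75, that is, when baseline > 1.75/0.75 = 2.33 mmol/L.

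| Assumed baseline (mmol/L) | Level after 25% rise (counts falsely) | Level after 25% fall | Does that fall reach 1.75? | Missed band (mmol/L) |
|---|---|---|---|---|
| 2.1 | 2.625 | 1.575 | yes | none |
| 2.3 | 2.875 | 1.725 | yes | none |
| 2.4 | 3.0 | 1.80 | no | >1.75 to 1.80 |
| 2.5 | 3.125 | 1.875 | no | >1.75 to 1.875 |
| 2.6 | 3.25 | 1.95 | no | >1.75 to 1.95 |

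**Step 4: when does calcium decide?** Two abnormal values are needed. If two or three of the other analytes are abnormal, laboratory TLS is met without calcium. If none is, calcium alone cannot make two. The calcium row changes the classification only when exactly one other analyte is abnormal.

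**Step 5: is the baseline use affected?** Section 4.1.2.4 applies the table to baseline chemistry, where no change from baseline exists. Only the value column can apply, so that classification is unaffected.

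**Step 6: the corrected cell.** With a 25% decrease, both calcium criteria point downward and coincide at a baseline of 2.33 mmol/L. Above that baseline, the change criterion adds the falls in the last column of the table, which the limit alone misses.

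**The case against.** The case for treating this as a minor slip has real force.

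- **The main criterion survives on the more plausible reading.** Under 'or', a calcium at or below 1.75 still counts. Section 4.1.2.4 supports 'or', and so does the appendix, which allows TLS to be identified at presentation and up to three days before therapy. A site that used the Value column alone would also classify low calcium against the limit correctly. The 1.40 mmol/L result therefore belongs to the less likely reading.
- **What remains under 'or' is narrow.** A missed case needs a baseline above 2.33 mmol/L, a fall into a small band, exactly one other abnormal analyte, and literal use of the cell. A false flag leads to an unnecessary admission or held dose, which errs on the cautious side.
- **Other safeguards do not depend on the cell.** Section 4.1.2.1 lets the investigator modify management. Table 19 schedules chemistry monitoring by tumor burden. For CLL/SLL, Section 4.1.2.3 acts on potassium or phosphorus alone at lower thresholds.
- **The statistical design does not use the table.** DLTs in Section 3.1.4 rest on grade and attribution, and no sample size or stopping rule in Section 10 refers to Table 21.

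All of this stands, and it limits the impact. None of it corrects the cell. Neither way of joining the two columns makes the printed row correct: it behaves as intended only if staff set the change cell aside, and the plan does not tell them to. Investigator discretion over management also leaves the definition used to classify events unchanged.

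**Conclusion.** The concern holds. The calcium change cell is wrong in direction, it sits in an operative safety criterion, and nothing elsewhere in the plan corrects it. It should be fixed, but it is not a fatal flaw.

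The practical effect is small. Under 'or', what is lost is a band of 0.05 mmol/L at an assumed baseline of 2.4 (1.80 − 1.75) and 0.125 mmol/L at 2.5 (1.875 − 1.75), and rises to 3.0 and 3.125 mmol/L count falsely. Under 'and', calcium effectively drops out of the definition. In either case, classification changes only when exactly one other analyte is abnormal. The number of patients affected is likely very small and cannot be derived from the documents. Sample size, DLT rules and planned analyses do not depend on the cell.

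The conclusion rests on the table as it reads in the public file. The row is complete and aligned, so a file-conversion error is unlikely, but it cannot be fully excluded.

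**What to change.** In Appendix E, Table 21, change the calcium entry under Change from baseline to a 25% decrease. Add one line below the table stating how the Value and Change columns combine. 'Or' is the choice consistent with Section 4.1.2.4.

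The cost is one table cell and one sentence in the next amendment. Dosing, sample size and analyses stay as they are, and there is no downside.
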